### 13.2 Sample size and accrual

The primary objective is to evaluate efficacy of ONC-201 with dietary MR in metastatic TNBC. The study is designed as a single-arm phase II trial. The primary endpoint is ORR. Secondary endpoints include CBR at 4 months, PFS, OS, safety, metabolic indices and CTC TRAIL-receptor expression. The null hypothesis is that the probability of overall response is no more than 0.1, *i.e.*,  $H_0: p \leq 0.1$ , and the alternative hypothesis is  $H_1: p \geq 0.25$ .

In this single arm study, a Simon's two stage design will be utilized. The null hypothesis that the true ORR is 0.1 will be tested against a one-sided alternative. The study will be powered to detect an ORR of 25% with the combination of ONC201 with a methionine-restricted diet, using a power of 80% and a type I error rate of 10%. The first stage sample size will be 13. After testing the combination on 13 subjects in the first stage, the trial will be terminated if 1 or fewer subjects respond. If the trial goes on to the second stage, a total of 34 subjects will be studied (*i.e.* additional 21 subjects will be recruited). If the total number responding or having ORR is less than or equal to 5, the combination of ONC201 with a methionine-restricted diet will be rejected.

The estimated total sample size for the study is 34 subjects.

One subject was enrolled to the ONC201 +MR diet prior to changing the dosing schedule. This subject will be replaced for efficacy analysis, but will be considered part of the safety analysis.

### **13.3 Analysis datasets**

Population	Definition
Evaluable for Safety	This will comprise all subjects who receive at least one dose of trial drug and either undergo at least one post-baseline assessment or die before any evaluation.
Evaluable for Efficacy	This will comprise all subjects who receive at least 80% of ONC201 + MR diet doses during the first two cycles of treatment (i.e., at least 9 doses of ONC201) and have at least one disease re-evaluation. Subjects who are not evaluable for response, however, will be replaced.

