## **4.2 General Guidelines**

Following registration, subject must have cycle 1 day 1 within 7 days. Issues that would cause treatment delays should be discussed with the Principal Investigator. If a subject does not receive protocol therapy or MR diet following registration, the subject may be replaced.

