## 6.2 ONC201 Dose Adjustments

The descriptions and grading scales found in the revised NCI CTCAE v5.0 will be utilized for dose delays and dose modifications

Criteria for disrupting treatment, dose modification, or discontinuation are listed in **Table 5**.

For subjects who do not tolerate the dosing schedule, dose adjustments are permitted in order to allow the subject to continue the study treatment.

Below are dose modifications (**Table 5**) for adverse events that are at least possibly, probably or definitely attributable to study drug, including: nausea, vomiting, diarrhea, neutropenia, and thrombocytopenia. If a patient experiences other adverse

events, or several adverse events and there are conflicting recommendations based on grade, the investigator will use the recommended dose adjustment that reduces the dose. Dose modifications will be made based on an adverse event that occurs any time during a cycle.

**Table 5: Dose adjustment rules for Adverse Events (AEs),** including nausea, diarrhea, neutropenia, thrombocytopenia, and other AEs. Alopecia does not require dose adjustments. Lymphopenia does not require dose adjustment unless clinically significant per treating physician.

CTCAE Grade	Management/Next Dose for ONC201
≤ Grade 2	No change in dose
Grade 3 or 4*	Hold until ≤ Grade 2. If resolved to ≤ Grade 2 within 7 days, resume dosing at 500mg if previously dosed at 625mg or resume dosing at 375mg if previously dosed at 500mg.** (See monitoring guidelines below)

\*Patients requiring a delay of ONC201 for >3 weeks must go off protocol therapy.  
Patients with grade 3 neutropenia associated with fever must also discontinue ONC201.  
\*\*Patients requiring > two dose reductions must discontinue ONC201.

Participants who experience an adverse event that requires a treatment delay or dose reduction should be monitored with appropriate laboratory testing or other clinical evaluation at least weekly until resolution; if the adverse event does not resolve within 3 weeks, the interval for testing may be reduced after consultation and written approval by the study PI.

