### **6.3 Protocol therapy discontinuation**

In addition to discontinuation from therapy related to toxicities as outlined in section 6.1, a subject will also be discontinued from protocol therapy and followed up per protocol under the following circumstances:

- Documented disease progression
- Discontinue methionine restricted diet for weight loss grade 2 or higher
- The treating physician thinks a change of therapy would be in the best interest of the subject
- The subject requests to discontinue protocol therapy, whether due to unacceptable toxicity or for other reasons
  - If a subject decides to prematurely discontinue protocol therapy ("refuses treatment"), the subject should be asked if he or she may still be

contacted for further scheduled study assessments. The outcome of that discussion should be documented in the medical records.

- A female subject becomes pregnant
- If protocol therapy is interrupted for >21 days.

Subjects will be removed from protocol therapy, and the site investigator notified, when any of the criteria listed above apply. The reason for discontinuation of protocol therapy will be documented on the eCRF in OnCore.

Subjects who discontinue protocol therapy will be followed every 3 months for 2 years after the end of treatment visit. Survival status and anti-cancer therapy (to include only first cancer directed therapy after study) will be collected from review of medical records or via telephone follow up.

If subjects discontinue study treatment prior to disease progression, scans during follow-up will be completed per standard of care, but RECIST measurements must be completed until disease progression or start of new anti-cancer therapy.

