#### **6.4      Evaluable subject**

**Evaluable for response:** Any subject who receives at least 80% of ONC201 doses during the first two cycles of treatment (i.e., at least 9 doses of ONC201) and have at least one disease re-evaluation will be evaluable for response. Dose reductions will not be included in this 80%, just number total doses taken will be included.

**Evaluable for toxicity:** Any subject who receives at least one dose of treatment on this protocol should be evaluable for toxicity. Safety will be assessed by NCI CTCAE v5.0.

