### 9.8.5 Objective Response Rate

The objective response rate is the proportion of all subjects with confirmed PR or CR according to RECIST 1.1, from the start of treatment until disease progression/recurrence (taking as reference for progressive disease the smallest measurements recorded since the start of treatment).

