### **13.6 Assessment of efficacy**

All subjects who have received at least 80% of ONC201 + MR diet during the first two cycles of treatment and have their disease re-evaluated will be evaluable for assessment of objective response.

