### **13.7 Data analysis plan**

#### **13.7.1 Analysis plans for primary objective**

ORR will be estimated according to RECIST 1.1, by dividing the total number of responders (complete plus partial responses plus CR or PR) or (CR or PR), respectively, by number of subjects with measurable disease and the exact 95% confidence interval will be provided. In evaluating ORR, subjects with missing data will be considered non-responders.

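### Section 13.3 replaces treated subjects who fail early, so treatment failures can leave the 1/13 and 5/34 response counts, and the plan does not say which denominator governs the primary ORR

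*Combined protocol and SAP*

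**What the plan says.** Section 6.4 sets the condition for response: "Any subject who receives at least 80% of ONC201 doses during the first two cycles of treatment", glossed as at least 9 doses, plus at least one disease re-evaluation. Section 13.3 uses the same threshold to define the efficacy set, but for ONC201 and diet together, and adds: "Subjects who are not evaluable for response, however, will be replaced". Section 13.6 repeats that subjects who meet the dose condition "and have their disease re-evaluated will be evaluable for assessment of objective response". None of the three makes an exception for the reason a subject falls short. Death before any evaluation is provided for only in the safety set of Section 13.3.

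Two other sections describe the ORR differently. Section 9.8.5: "The objective response rate is the proportion of all subjects with confirmed PR or CR". Section 13.7.1 divides by subjects with measurable disease, which is an entry criterion (3.1.2), and adds: "In evaluating ORR, subjects with missing data will be considered non-responders".

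Section 13.2 gives the decision rule: stop after 13 if 1 or fewer respond, and reject the combination if 5 or fewer of 34 respond. It does not name the set to be counted. Section 13.1 sets a study maximum of 34. Section 4.2 has its own provision: "If a subject does not receive protocol therapy or MR diet following registration, the subject may be replaced".

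**The concern.** Whether a subject is counted depends partly on what happens after treatment starts. A subject who dies before a scan, or deteriorates without one, leaves the set and is replaced. So is one who stops for progression or toxicity before the ninth dose. Some of these stops are required by the protocol itself, as in Section 6.2: "Patients with grade 3 neutropenia associated with fever must also discontinue ONC201". Section 6.3 keeps such subjects under assessment, since "RECIST measurements must be completed until disease progression or start of new anti-cancer therapy", yet a documented progression in a subject with fewer than nine doses still falls outside the efficacy set.

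The margins are thin. Suppose 2 of the first 13 treated subjects are replaced, and one of two responders is a replacement. The evaluable count is 2/13 (continue) and the all-treated count is 1/13 (stop). The trial is open label and single arm, and staff could cite the protocol for either count. A choice made after the outcomes are known could not be repaired.

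**Working it through.** **Timing.** Section 5.2 gives ONC201 on days 3, 4, 10, 11, 17 and 18 of a 21-day cycle. Over two cycles the dose days are 3, 4, 10, 11, 17, 18, 24, 25, 31, 32, 38 and 39, so the ninth dose falls on day 31. The first scheduled scan (Section 7, note 10) is within 7 days before cycle 4. Cycle 4 day 1 is day 1 + 63 = 64, so the window is days 57-64. A two-week hold loses 4 of the 12 doses and leaves 8, which is below the threshold.

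**The plan's own design.** Inputs from Section 13.2: n1 = 13, r1 = 1, n = 34, r = 5, null 0.10, alternative 0.25.

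- Stage 1 stop under the null: 0.9^13 + 13 × 0.1 × 0.9^12 = 0.254 + 0.367 = 0.621.
- P(pass) = sum over x = 2 to 13 of P[Bin(13, p) = x] × P[Bin(21, p) ≥ 6 − x].
- At p = 0.10 this is 0.0957; at p = 0.25 it is 0.811. The stated 10% and 80% are met.

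**Replacement, accrual to 34 evaluable.** Let q be the fraction of treated subjects replaced and e their response rate. Both are assumptions; the documents give neither. If the all-treated ORR is 0.10, the evaluable ORR is (0.10 − q·e)/(1 − q), and P(pass) is evaluated at that rate.

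| q | Evaluable ORR, e = 0 | Type I error, e = 0 | Type I error, e = 5% | Type I error, e = 10% |
|---|---|---|---|---|
| 5% | 10.5% | 11.5% | 10.5% | 9.6% |
| 10% | 11.1% | 13.9% | 11.6% | 9.6% |
| 20% | 12.5% | 20.3% | 14.4% | 9.6% |

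Filling 34 evaluable places takes on average 34/(1 − q) = 35.8, 37.8 or 42.5 treated subjects, which is above 34.

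**Replacement, 34 as a hard cap on treated subjects (e = 0).** Stage 1 is read at the 13th evaluable subject, who is the t-th treated with probability C(t−1, 12)(1−q)^13 q^(t−13). Responders among those 13 follow Bin(13, 0.10/(1−q)). The remaining 34 − t treated subjects each respond with probability 0.10. Passing needs at least 2 responders at stage 1 and at least 6 in total. Summing over t gives type I error 9.9%, 10.2% or 10.8% at q = 5%, 10% or 20%. The final count is unaffected because the excluded subjects add no responders; only the stage 1 look shifts.

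**If the null refers to evaluable subjects**, p = 0.10 in that set by definition and type I error stays 9.6% for any q.

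**The case against.** The strongest reply is that the plan can be read coherently. Sections 13.3 and 13.6 define the evaluable set, 10% and 25% apply to it, and the missing-data rule of 13.7.1 works inside it. That rule would still have something to act on: Section 9.7 allows a non-evaluable result when target lesions are not all assessed, and a first response followed by a non-evaluable assessment may never be confirmed. This reading is tenable and removes the inflation. But no section states it, it leaves the wording of 9.8.5 unreconciled, and it yields an ORR for a subset selected partly by outcome.

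The exposed group is also limited. A re-evaluation need not be the scheduled CT, and a subject who progresses after the ninth dose with any re-evaluation stays in as a non-responder. Entry requires ECOG 0 or 1 and a life expectancy above 12 weeks. Section 1.5.4 reports no drug-related toxicity above grade 1 in ten patients, though on a three-weekly schedule. These points argue for a modest q. They do not supply a value or an exception.

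Two stronger readings are tempting and should not be drawn. A reader might conclude that the true type I error is about 20%. That needs q = 20%, no responders among those replaced, an all-treated null and accrual beyond 34 treated, none of which the documents establish. A reader might also take 4.2 as contradicting 13.3. It does not: it permits replacement of subjects who receive no therapy or diet, without confining replacement to them.

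**Conclusion.** The point stands as a gap in the definition of the primary analysis. As written, 13.3 lets treated failures be replaced in the 1/13 and 5/34 counts, and the documents do not settle whether that set or the wider one of 9.8.5 and 13.7.1 governs. The stated design figures are correct; what is undefined is whom they count.

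The effect on type I error runs from none to large, depending on unstated readings. There is none if the null refers to evaluable subjects, or if replaced subjects respond at 10%. It is small if 34 caps treated subjects. It is material if accrual continues to 34 evaluable and the replaced subjects rarely respond. Even where the error rate holds, the reported ORR would not describe all treated patients. The set should be fixed in writing before the stage 1 count is taken.

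**What to change.** In 13.3, stop replacing subjects who started study treatment and then progress, die, deteriorate or stop for toxicity. Count them as non-responders in the primary ORR and in both decision counts, unless a confirmed CR or PR is documented before progression or new therapy. The simplest form:

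- The primary set is all subjects who start ONC201 or the MR diet on the current schedule. Including diet starters matters because the diet begins on day 1 and ONC201 on day 3.
- Replacement is kept for subjects who start neither (4.2) and for the one subject enrolled before the schedule change (13.2).
- The dose-threshold set becomes a sensitivity analysis.
- Sections 13.2 and 13.7.1 name the set; 6.4, 9.8.5 and 13.6 are aligned with it.
- Section 13.1 says whether its maximum of 34 counts treated or analysed subjects.
- The plan states that 10% and 25% refer to the named set.

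The cost is wording, since 6.3 already requires RECIST measurements after an early stop, and probably a lower reported ORR. If 10% and 25% were meant for evaluable subjects and the others never respond, the all-treated rates become 0.25(1 − q) = 23.75%, 22.5% or 20% at q = 5%, 10% or 20%. Power with the same cut-offs then falls from 81.1% to 77.1%, 72.5% or 61.4%, and type I error to 7.9%, 6.4% or 4.0%. In that case the power should be restated.

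Two minor inconsistencies can be tidied in the same edit but are separate from this point: 80% of 12 doses is 9.6, whereas 9 of 12 is 75%; and 6.4 counts ONC201 only, whereas 13.3 and 13.6 add the diet.

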### **13.4 Assessment of safety**

Any subject who receives at least one dose of treatment on this protocol should be evaluable for toxicity. Safety will be assessed by NCI CTCAE v5.0.

### **13.5 Demographic and baseline characteristics**

Descriptive statistics will be provided to summarize demographics and baseline characteristics parameters. Categorical data will be summarized as frequency and its corresponding percentage. For continuous data, frequency (n), mean, standard deviation, median (as appropriate), minimum, and maximum will be provided for each of the parameters.

### **13.6 Assessment of efficacy**

All subjects who have received at least 80% of ONC201 + MR diet during the first two cycles of treatment and have their disease re-evaluated will be evaluable for assessment of objective response.

### **13.7 Data analysis plan**

#### **13.7.1 Analysis plans for primary objective**

ORR will be estimated according to RECIST 1.1, by dividing the total number of responders (complete plus partial responses plus CR or PR) or (CR or PR), respectively, by number of subjects with measurable disease and the exact 95% confidence interval will be provided. In evaluating ORR, subjects with missing data will be considered non-responders.

### 13.7.2 Analysis plans for secondary objectives

PFS and OS will be summarized using Kaplan-Meier estimates of the median survival times. Point estimates as well as 95 % confidence intervals will be provided. PFS based on degree of AR expression by IHC (AR >0% vs. AR  $\geq$ 10%) will be compared using the log-rank test. Additional exploratory analyses using proportional hazards model to control for other factors may be performed.

CBR at 4 months will be estimated according to RECIST 1.1, by dividing the total number of responders (complete plus partial responses plus CR or PR or stable disease (SD)), by number of subjects with measurable disease and the exact 95% confidence interval will be provided. In evaluating CBR, subjects with missing data will be considered non-responders. Also, duration of response (DOR) will be measured using Kaplan-Meier methodology. A 95% confidence interval will be provided for the median duration of response. Subjects who do not relapse will be censored at the day of the last objective tumor assessment. In evaluating response duration, non-responders will be excluded from analysis.

In addition, correlation analyses will be performed to assess the expression of TRAIL receptor in CTCs prior, during and upon progression of disease. Formal statistical tests will be performed based on the outcome types and the biomarker quantification.

Safety and Tolerability by NCI CTCAE v5.0 will be assessed by frequency tables. Also, metabolic indices in patients with metastatic TNBC treated with ONC-201 and a methionine-restricted diet will be assessed by frequency tables and descriptive statistics.

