### 9.8.6 Progression-Free Survival

A measurement from the date of treatment initiation until the criteria for disease progression is met as defined by RECIST 1.1 or death occurs. Subjects who have not progressed will be right-censored at the date of the last disease evaluation.

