### 9.8.7 Overall Survival

Overall survival is defined by the date of treatment initiation to date of death from any cause.

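### Section 13.7.2 names no population for PFS and OS, and the only efficacy set in 13.3 would drop early deaths and count guaranteed survival time, mainly in OS

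*Combined protocol and SAP*

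**What the plan says.** Section 13.7.2 gives the method for the two time-to-event endpoints, "PFS and OS will be summarized using Kaplan-Meier estimates of the median survival times", with confidence intervals. It gives no population, landmark or delayed entry.

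Section 13.3 defines two sets. The safety set takes anyone with at least one dose and expressly keeps those who die before any evaluation. Of the efficacy set it says "This will comprise all subjects who receive at least 80% of ONC201 + MR diet doses during the first two cycles of treatment", and it then adds the condition "i.e., at least 9 doses of ONC201) and have at least one disease re-evaluation". It goes on: "Subjects who are not evaluable for response, however, will be replaced".

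Both clocks start at the beginning of treatment:
- OS (9.8.7): "Overall survival is defined by the date of treatment initiation to date of death from any cause".
- PFS (9.8.6): "A measurement from the date of treatment initiation until the criteria for disease progression is met as defined by RECIST 1.1 or death occurs". Subjects without progression are censored at their last disease evaluation.

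Two other places bear on which set applies. Section 13.6 says that subjects meeting the exposure and re-evaluation conditions "will be evaluable for assessment of objective response", and 6.4 likewise ties evaluability to response. Section 13.2 replaces one subject, enrolled before the dosing schedule changed, for the efficacy analysis but keeps that subject for safety. So the plan sorts subjects into efficacy and safety, with no third group.

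**The concern.** Entry to the efficacy set is decided after time zero. A subject who dies before the 9th dose, or before any re-evaluation, cannot be in it. Treatment also stops at documented progression (6.3), so progression documented before the 9th dose excludes a subject as well. If PFS and OS are estimated in this set from treatment initiation, the curves open with a stretch in which an OS event is impossible by construction, and the subjects with the earliest events have been replaced by others.

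A response proportion can absorb early failures by counting them as non-responders, as 13.7.1 does for missing data. A Kaplan-Meier curve cannot recover events in subjects who are not in it. With no control arm, no comparison curve carries the same bias. If the population is left open in an open-label trial, it could also be chosen after the data are known.

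**Working it through.** **Plan's own figure.** The plan states no median, event count or sample size for PFS or OS. Its only sized figure is the Simon design for ORR in 13.2 (13 subjects, stop at 1 or fewer responses; 34 subjects, reject at 5 or fewer; 10% against 25%). By exact binomial calculation this has type I error 0.0957 and power 0.811, so it reproduces. Nothing below affects it.

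**When entry to the efficacy set is decided.**
- Dosing days in 5.2, carried over two 21-day cycles, are 3, 4, 10, 11, 17, 18, 24, 25, 31, 32, 38, 39. The 9th scheduled dose is on day 31, so an included subject has survived at least 30 days from day 1. (9 of 12 doses is 75%, while 80% of 12 is 9.6; the two thresholds in 13.3 need reconciling, but the timing hardly changes.)
- The study calendar puts the first scan within 7 days before cycle 4, about days 57-64, or 56-63 days after the start.

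**OS.** Inputs: median m = 13 months (Section 1.1), exponential survival (assumption), guaranteed time L = 30 or 63 days, 30.4375 days per month.
- L = 30/30.4375 = 0.99 months, or 63/30.4375 = 2.07 months.
- Share dying before L = 1 - 2^(-L/m).
- Median from treatment start among those alive at L = m + L.
- 6-month OS among those alive at L = 2^(-(6-L)/m).

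| True median | L (days) | Die before L | Median reads | Shift | 6-month OS, all treated | 6-month OS, set |
|---|---|---|---|---|---|---|
| 13 months | 30 | 5.1% | 14.0 | +8% | 72.6% | 76.5% |
| 13 months | 63 | 10.4% | 15.1 | +16% | 72.6% | 81.1% |
| 9 months (assumed) | 30 | 7.3% | 10.0 | +11% | 63.0% | 68.0% |
| 9 months (assumed) | 63 | 14.7% | 11.1 | +23% | 63.0% | 73.9% |
| 6 months (assumed) | 30 | 10.8% | 7.0 | +16% | 50.0% | 56.0% |
| 6 months (assumed) | 63 | 21.3% | 8.1 | +34% | 50.0% | 63.5% |

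At 13 months, filling 34 evaluable places would take 34/0.949 = 35.8 to 34/0.896 = 38.0 treated subjects. About 2 to 4 deaths would be missing from the curve.

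**Lower early hazard.** Entry requires life expectancy above 12 weeks (3.1.9) and ECOG 0 or 1 (3.1.6). Suppose the death hazard before L is a fraction h of the later hazard k. The true median is then ln2/k + L - hL, the median in the set is ln2/k + L, and the shift is hL. With h = 0.5 (assumption), L = 63 days gives 1.03 months, which is +8% at 13 months; L = 30 days gives 0.49 months, +4%.

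**PFS.** Simulation with scans every 63 days, true median 2, 3 or 4 months, and 10%, 25% or 50% of those progressing before the first scan dying or leaving unscanned (all assumptions). In the all-treated curve these subjects count as events at their progression time. 4-month PFS in the set = all-treated 4-month PFS / (1 - excluded share):
- Median 3, 25%: 0.621/(1 - 0.095) = 0.686.
- Median 2, 50%: 0.488/(1 - 0.257) = 0.657.
- Median 4, 10%: 0.699/(1 - 0.030) = 0.721.

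Over all nine cases 4-month PFS rises by 2 to 17 points. The median stays at 4.1 months when the true median is 3. It moves up one scan interval (2.1 to 4.1, or 4.1 to 6.2) when the true median is 2 or 4, values that lie just short of a scan date.

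**The case against.** The strongest reply is that the plan never says PFS and OS use the efficacy set. Sections 6.4, 13.3 and 13.6 attach evaluability and replacement to response. The definitions in 9.8.6 and 9.8.7 carry no evaluability condition. Section 6.3 follows survival in everyone who stops therapy. For CBR, 13.7.2 itself divides by subjects with measurable disease, an entry criterion, rather than by the efficacy set. A reader might infer that the plan commits itself to overstated PFS and OS; the documents do not support that. They leave the population unstated, with one efficacy set to fall back on.

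Four points on size and consequence also stand:
- A re-evaluation need not be the scheduled scan, so an earlier unscheduled one qualifies. The firm guarantee is to about day 31, not week 9.
- The 6- and 9-month medians are not in the documents, so the largest shifts cannot be presented as expected.
- Progression at the first scan still counts as a PFS event, so a claim that both medians shift goes too far.
- The 13-month figure is disease background in 1.1. The plan does not say that PFS or OS will be compared with it.

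What the reply does not do is supply a population. Read as excluding PFS and OS from the efficacy set, 13.3 leaves them with none, and the same amendment is needed.

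**Conclusion.** The point holds as a gap with a foreseeable bias. If the efficacy set is used from treatment initiation, the direction for OS is upward. At the protocol's 13-month median and under exponential survival, the size is about 1.0 month (+8%, day 30) to 2.1 months (+16%, day 63). The relative shift is larger if the true median is shorter, which is an assumption. For guaranteed time alone these are probably upper figures, given the 12-week life-expectancy criterion. Further selection from leaving out survivors who took too few doses is not modelled. For PFS the effect is weaker: early rates rise, and the median may or may not change.

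These are descriptive secondary endpoints with no decision rule, so the plan should be amended, but the trial's conclusion on ORR does not depend on it.

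**What to change.** In 13.3, add an all-treated set: every subject with at least one ONC201 dose on the current schedule, with no dose-count or re-evaluation condition. This keeps the exclusion in 13.2 of the subject enrolled before the schedule change.

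In 13.7.2, state that OS and PFS are analysed in this set from treatment initiation. For PFS, also:
- count a death without any re-evaluation as an event, which 9.8.6 already allows;
- report how many treated subjects have no post-baseline scan and are therefore censored at baseline under 9.8.6, since the new set alone does not restore their information;
- add a sensitivity analysis that treats those subjects as early failures.

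Label any PFS or OS curve in the evaluable set as supportive, or start it at a landmark.

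The cost is a few sentences. Section 6.3 already requires survival follow-up every 3 months for 2 years after treatment ends. RECIST measurement continues only until progression or new anti-cancer therapy, with off-treatment scans per standard of care, so PFS data will be less complete than OS data; this is why the sensitivity analysis is needed. The estimates may come out slightly less favourable.
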